Thyroid Stimulating Hormone (TSH)	11.12.2020	X	N/A	N/A	N/A	*	N/A	X	N/A	X	X

Table 2. Schedule of safety labs. 'X'= Test performed; N/A = Not applicable. % This visit only occurs for participants who ended Tofacitinib treatment at Visit 7. E = Extension arm only visits * Follow-up required only if Screening Visit results are positive or participant is known thyroid dysfunction . ^ For females if not surgically sterile or two years post-menopause.

Visit 7 Considerations for the 16-week Endpoint.

If a participant misses 15% or more of Tofacitinib doses (3 or more pills) in the 7 days before a scheduled Visit 7 for any reason, Visit 7 will be rescheduled to ensure 7 days of compliant study drug intake before this endpoint visit. This may be outside the original +/- 3 days window for Visit 7. Treatment will not be extended beyond 18 weeks before a Visit 7 occurs. This will be recorded as a protocol deviation.

Similarly, if a participant reports a confounding adverse event within 7 days of Visit 7, Visit 7 will be rescheduled so that at least 7 days have passed since the condition was resolved. This may be outside the original +/- 3 days window for Visit 7. Treatment will not be extended beyond 18 weeks before a Visit 7 occurs. This will be recorded as a protocol deviation.

Extension Arm – Study Drug.

Some participants may not respond, or may not achieve a full response, to Tofacitinib by the end of the 16-week trial. Participants who are likely to benefit from an extension of Tofacitinib will be initially identified by the study doctor at their 8-week visit (Visit 5) using the criteria below, but may be identified as a candidate for the extension trial at subsequent visits at the study doctor's discretion if the criteria are met. Additionally,

participants must remain in good health standing and have no study doctor concerns that would preclude study continuation.

1. Alopecia areata (min. initial qualifying SALT score ≥ 25): Participant shows any decrease in their SALT score from the Baseline score, but SALT score is still ≥ 5 at the 8-week appointment.
 - In cases of alopecia totalis, observable improvement in any hair re-growth on the body would constitute a basis for Extension Arm qualification, such as eyelash or eyebrow re-growth.
 - All cases of alopecia areata present for ≥ 5 years by parent or clinician report will be invited to participate in the Extension Arm, even if no improvement decrease in SALT score is noted by 8 weeks.

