definitely related to the investigational agent, and 3) it suggests that the study places participants at a greater risk of harm (including physical, psychological, economic, or social harm) than was previously recognized. Some AE/SAEs may also be flagged as UAPs, if all three of these criteria are met; however, UAPs can also include study-level events or outcomes encompassing more than one AE or participant.

When any SAE or UAP is discovered by a study coordinator or doctor, that personnel will immediately notify all three study PIs. The contact PI, [name], will be responsible for prompt reporting of any SAE or UAP to the appropriate agents as follows:

- 1) **Fatal or life-threatening SAE:** PIs notify COMIRB, NIAMS, and the DSMB within 48 hours.
- 2) **Possibly or Definitely related to Tofacitinib SAE:** PIs notify COMIRB, NIAMS, and the DSMB within 48 hours.
- 3) **All other SAEs:** PIs notify NIAMS and the DSMB within 48 hours and COMIRB within 5 days.
- 4) **Any UAP:** PIs notify NIAMS and the DSMB within 48 hours and COMIRB within 5 days.

Safety and Adverse Event Reporting.

Monthly Progress and Safety Reports will be compiled by the clinical coordination team for review by the appropriate parties. Progress and Safety Reports will include information regarding recruitment and enrollment status, comparison of targeted to actual enrollment, retention status, and demographic information of participants. These reports will also detail participant adherence to study protocol, which will be evaluated by verbal reports of pill counts at each study visit. Finally, Monthly Progress and Safety Reports will contain summarized AE information including: 1) a list of all AEs reported, including their classifications, actions taken, and outcome 2) a list of all symptoms and their frequency reported by participants, 3) all incidences of laboratory values considered out-of-range for an individual with Down syndrome, 4) a list of all SAEs reported, including their classifications, actions taken, and outcome, and 5) information about any participant deaths, including the cause of death. Monthly Progress and Safety Reports will not include subject- or group-identifiable material. Each report will only include the Study ID.

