- 6) Any medical or personal event(s) or participant non-adherence resulting in missed Tofacitinib doses totaling 15% (34 doses) or more of total study drug for the 16-week treatment period (224 doses). At the Endpoint Visit (Visit 7), this calculation will be re-applied with the true number of doses the participant had the opportunity to take within the allowable +/- 3 day study visit window (e.g., 221 or 222 doses for a participant whose Endpoint visit is scheduled one day earlier than 16 weeks) to confirm the adherence rate for the actual treatment period. For participants in the Extension Arm, participants missing more than 15% of total doses at E28 will be terminated from the study.
- 7) Two missed study visits without study doctor approval.
- 8) If at any point during the study a participant fails to return communication with a study coordinator after 3 consecutive attempts made using at least 2 forms of contact provided by the participant and/or study partner, then [name] will make at least one attempt to contact the participant using their preferred method of contact. After a total of five unreturned communications, the participant will be considered lost to follow-up and no further contact attempts will be made.
- 9) A study doctor may discontinue a participant from Tofacitinib for any reason, including noncompliance, at the study doctor's discretion. It should be noted that discontinuation of Tofacitinib, for whatever reason, does not necessarily constitute withdrawal from study. A study doctor, in consultation with all PIs, may advise a participant and their study partner to discontinue Tofacitinib temporarily while remaining in the study.
- 10) Alternatively, a study doctor may decrease the dosage to 5 mg once daily. These determinations will be considered by the PIs on a case-by-case basis.
- 11) Participant experiences an SAE definitely related to Tofacitinib.

Participants who are removed from study for reasons other than an adverse drug reaction may, if they choose, return and start the entire study over again (beginning with the Pre-screening phone interview or a Screening visit, as appropriate), at the discretion of study staff and after at least 21 days have passed since taking their last dose of Tofacitinib.

This entire clinical trial, including the Extension Arm, will be stopped prior to its completion if:

- 1) the intervention is associated with adverse effects that call into question the safety of the intervention;

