From a dermatology standpoint, this trial is considered a 'bucket trial', so designated because we will include individuals with DS and diverse active immune skin conditions. We aim to enroll at least 10 participants during the initial phase, before performing a qualitative interim analysis and continuing with 30 additional participants. Up to 15 participants may be included in the interim analysis. Based on our ongoing cohort study and epidemiological data of skin diseases in people with DS (24, 25, 116-118), we expect to enroll five predominant conditions: AD, AA, HS, psoriasis, and vitiligo (*Figure 1B*), but will accept other immune skin conditions according to our dermatologists' expertise. Being an open-label, proof-of-concept study, all participants will receive Tofacitinib at 5mg BID for 16 weeks. We will evaluate changes from baseline to 16 weeks in: 1) Investigator's Global Assessments (IGAs), 2) Dermatology Life Quality Index (DLQI) (119), and 3) Disease-specific metric scores. The IGA and DLQI will serve as 'composite endpoints' to capture overall clinical improvement in a disease-agnostic fashion. Additionally, each participant will be monitored using the relevant accepted disease-specific metric scoring systems, for example: Eczema Area and Severity Index (EASI) for AD, Severity of Alopecia Tool (SALT) for AA, Modified Sartorius Score (MSS) for HS, Psoriasis Area and Severity Index (PASI) for psoriasis, and Vitiligo Extent Tensity Index (VETI) for vitiligo (120-124).

These measures are all well-validated and widely used in clinical trials related to skin disease, and our team of dermatologists has extensive experience with all these metrics. We define success of this endpoint as statistically significant *percentage reduction* in a) IGA values, b) DLQI values, and c) disease-specific scores between baseline and 16 weeks as defined by a two-sided, paired Student's t-test.

Research Methods for Specific Aim 4. To characterize the impact of JAK inhibition on cognition and quality of life in Down syndrome.

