Method: This number is based on published safety data for Tofacitinib for the treatment of rheumatoid arthritis in the general population, which indicates a rate of 9.4 SAEs per 100 patient years. Given that our trial aims to enroll 47 participants for 16 weeks of treatment (though we anticipate up to seven participants would be lost to attrition at various times during the treatment course) for a maximum total of 14.5 patient years of treatment, a comparable number of SAEs is 1.36.

Specific Aim 2. To determine the impact of JAK inhibition on the immune dysregulation caused by trisomy 21.

The overall goal of our data analysis plan in this Aim is to define which immune processes dysregulated by T21 can be normalized by Tofacitinib treatment, i.e. returned to values observed in typical people. Importantly, data shown in this proposal demonstrate that we have already defined the directionality and average magnitude of the change between people with and without T21. For example, we determined that IFN scores are significantly higher in people with DS (*Figure 3C*) and expect that Tofacitinib will reduce these values. Whereas some of the features dysregulated by T21 may be normalized by Tofacitinib treatment, others may not, and this will provide an important mechanistic insight to understand the molecular underpinnings of immune dysregulation in DS. Accordingly, the endpoints associated with this Specific Aim focus on effects of Tofacitinib (16 weeks of treatment) on four classes of molecular markers of immune dysregulation:

Primary Endpoint: Change in IFN scores in the transcriptome of white blood cells.

Endpoint Definition: Statistically significant reduction in average IFN scores between baseline and 16 weeks as defined by a two-sided, paired Student's t-test.

Method: To determine the impact of Tofacitinib on IFN scores, a two-sided, paired Student's t-test will be used to compare baseline and 16 weeks of treatment for participants with good compliance with the study drug (2 or fewer missed pills) and without a confounding reported adverse event in the 7 days prior to the Visit 7 endpoint. With 40 participants, we have 80% power to detect an effect size of 0.45 with a p-value <0.05, as calculated by G*Power software.

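### Adherence is taken from verbal reports of pill counts with no check described, yet a difference of one reported pill (2 versus 3 of 14) decides whether Visit 7 is moved and whether the filter for the primary IFN test is met

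*Combined protocol and SAP*

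**What the plan says.** The only adherence method stated for the 16-week phase is in Section IV.C, Safety and Adverse Event Reporting: the monthly reports cover "participant adherence to study protocol, which will be evaluated by verbal reports of pill counts at each study visit".

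Three rules elsewhere use pill totals:

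- **Timing of the endpoint visit** (Section IV.C, Visit 7 Considerations for the 16-week Endpoint). The trigger reads: "If a participant misses 15% or more of Tofacitinib doses (3 or more pills) in the 7 days before a scheduled Visit 7". The visit is then rescheduled so that 7 compliant days precede it. The limit is: "Treatment will not be extended beyond 18 weeks before a Visit 7 occurs".
- **Analysis filter** (Section VII, Specific Aim 2, primary endpoint Method): the IFN test uses "participants with good compliance with the study drug (2 or fewer missed pills) and without a confounding reported adverse event" in the 7 days before Visit 7. The cytokine score and kynurenine endpoints carry the same filter.
- **Individual stopping rule 6** (Section IV.C, Participant Discontinuation and Trial Stopping): "missed Tofacitinib doses totaling 15% (34 doses) or more of total study drug for the 16-week treatment period (224 doses". The denominator is recalculated at Visit 7 for the doses the participant could actually have taken.

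Medication record logs and monthly phone check-ins are named in the Monitoring Only Extension Arm text. Nothing says they are compared with the verbal count. A guardian or study partner must attend every visit.

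**The concern.** The rules need a count that is right to the pill, and rule 6 even adjusts its denominator by two or three doses. The numerator is a figure given aloud. No staff or pharmacy count of returned tablets, drug level or electronic monitoring is described.

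Errors are more likely in one direction. Reporting 3 misses in the last week postpones the endpoint visit, and reporting 34 overall meets a stopping rule, so both give some reason to report fewer. Many participants depend on a partner, who may not have seen every dose.

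At stake is the make-up of the primary analysis set. The filter is meant to keep out people sampled while under-exposed. Misses that go unreported let them in and pull the mean IFN change toward zero. The same weakness affects rule 6.

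**Working it through.** **Inputs.** Twice-daily dosing (Section IV.C, Specific Aim 3 methods: "all participants will receive Tofacitinib at 5mg BID for 16 weeks"), so 14 doses in 7 days and 224 in 16 weeks. The 15% thresholds are in Section IV.C. N = 40, effect size 0.45, two-sided 0.05 and 80% power are in Section VII.

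**1. Do the plan's thresholds reproduce?** Yes.

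- 7-day window: 0.15 × 14 = 2.1, so the first whole count at or above 15% is 3. One missed is 1/14 = 7.1%, two is 2/14 = 14.3%, three is 3/14 = 21.4%. This agrees with 3 or more for rescheduling and 2 or fewer for the filter.
- Whole period: 0.15 × 224 = 33.6, rounded up to 34 (33/224 = 14.7%, 34/224 = 15.2%).

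The boundary therefore lies between 2 and 3 reported pills. This holds for twice-daily dosing. Section IV.C also allows a reduction to once daily. Then 7 doses fall due in 7 days and 2 missed is 2/7 = 28.6%, so the fixed count and the 15% figure no longer agree and the passages must be reconciled.

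**2. Does the stated power reproduce?** For a paired t-test, T is noncentral t with n − 1 = 39 degrees of freedom and noncentrality d√n, and power = P(|T| > 2.023). With d = 0.45, d√40 = 2.846 and power is 79.3%. This matches the stated 80% to within rounding, so the sample-size statement is not in error.

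**3. Effect of under-reporting (assumed shares and effects; the documents give none).** If k of 40 analysed participants keep a fraction r of the effect, the mean effect is 0.45 × [(40 − k) + k·r]/40. The SD is left unchanged.

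| k of 40 | r | Mean effect (SD) | Exact power |
|---|---|---|---|
| 0 | – | 0.450 | 79.3% |
| 4 | 11/14 | 0.45 × (36 + 3.143)/40 = 0.440 | 77.5% |
| 2 | 0 | 0.45 × 38/40 = 0.4275 | 75.1% |
| 4 | 0 | 0.45 × 36/40 = 0.405 | 70.5% |
| 8 | 0 | 0.45 × 32/40 = 0.360 | 60.3% |

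The row with r = 11/14 represents a true count of 3 missed reported as 2, with effect taken as proportional to doses. The rows with r = 0 represent gross concealment. Allowing for the extra variance from mixing responders and non-responders lowers the r = 0 rows slightly, to 74.7%, 69.7% and 58.9%.

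**The case against.** Several points on the other side stand.

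- **A reader might infer that a single missed pill is decisive.** It is not: 1/14 is 7.1%, and two misses are allowed. Only a one-pill difference at the 2-versus-3 boundary matters.
- **A reader might infer that a third missed pill removes the participant from the primary set.** It first moves Visit 7, after which the filter can be met. Membership is lost only if compliance is not reached within the 18-week limit.
- **A reader might attach the fall to about 70% power to the one-pill error.** That figure needs 4 of 40 with no effect at all. A 3-reported-as-2 error in 4 of 40 leaves about 77.5%.
- **A reader might infer that the safety rate is distorted.** Research Methods for Specific Aim 1 takes the 14.5 patient-years from planned treatment time, not pills taken. Reported misses do not enter that denominator.
- **A tablet count cannot date misses.** True. It gives the total since dispensing, whereas the filter concerns the last 7 days.
- **Some safeguards exist.** A partner attends each visit, logs are mentioned in the extension text, and what is reported is a pill count, not an impression. The accurate statement is that no verification is described, not that none takes place.
- **The incentive to under-report is limited.** The consequence in the last week is only rescheduling. Those removed for reasons other than an adverse drug reaction may be allowed to restart.
- **Dilution works against a positive IFN finding**, so it would not create a false success.

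These points narrow the concern. They do not supply a check on the count that defines the primary analysis set.

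**Conclusion.** The point holds as a design weakness that should be corrected. Verbal report is the only adherence method stated for the 16-week phase, no verification is described, and three rules depend on the result. The thresholds are consistent for twice-daily dosing; the weakness is in how the count is obtained.

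The harm is dilution of the primary IFN effect and a less reliable 34-dose rule. Its size is unknown. Under the assumptions shown, the loss of power runs from under 2 points (79.3% to 77.5%) for small misreports to about 19 points (79.3% to 60.3%) if 8 of 40 analysed participants had no effect. The documents give no evidence on which of these is closer.

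**What to change.** In Section IV.C, Safety and Adverse Event Reporting, replace verbal reports with a count of returned tablets by staff or pharmacy at each in-person visit, reconciled with tablets dispensed. At teleresearch visits, use a counted photo or video. Then state how the count is used:

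- **Rule 6:** use the reconciled count directly.
- **Visit 7 rescheduling and the Specific Aim 2 filter:** use a dated study-partner log for the last 7 days, cross-checked against the count since last dispensing. If the count shows 2 or fewer missed in total, no more than 2 can fall in the last 7 days and this part of the filter is confirmed. If log and count disagree, raise a query.

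No threshold changes. The Investigational Pharmacy already supplies the drug, so the cost is bringing the bottle and a few minutes per visit. Some participants may be reclassified as non-compliant. The 7-day classification will still rest partly on the partner's log, but on one that can be contradicted.

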Figure 5. Trisomy 21 induces the kynurenine pathway. **A.** Volcano plot showing results of a plasma metabolomics experiment on 120 participants, 72 of them with T21. **B.** Overview of tryptophan catabolism pathways. **C.** Quinolinic acid (QA) is significantly elevated in plasma of people with DS. **D.** RNA-seq shows that *IDO1* is overexpressed in white blood cells from people with DS. **E.** Spearman correlation analyses revealed strong association between activation of the kynurenine pathway and circulating levels of cytokines such as TNF α measured in the same plasma

neuroinflammatory phenotype of DS (90-98) may have therapeutic benefits, even in adults. Given the well-documented negative impact of hyperactive IFN signaling on brain function, from excessive synapse pruning by IFN-activated microglia to global impairments in cognitive function upon acute IFN α administration (99-106), **we hypothesize that reducing IFN signaling via JAK inhibition could improve cognition and behavior regulation in DS**. Of note, Tofacitinib was shown to cross the blood-brain barrier in mice (107). Thus, we will assess changes in selected cognition and overall quality of life metrics for individuals with DS upon JAK inhibition.

IV. Research Methods

B. Outcome Measure(s):

Name. Evaluate the safety of Tofacitinib in people with DS.

Type. Primary Endpoint.

Time Frame. Baseline through 16 weeks.

Brief Description. Adverse events (AEs) will be recorded, classified, and closely monitored by study coordinators and doctors. Based on published safety data, we calculate that we should have no more than two serious adverse events (SAE) definitely related to treatment over the course of 16-weeks in order to demonstrate comparable safety to the typical population.

Name. Change in IFN scores in the transcriptome of white blood cells.

Type. Primary Endpoint.

Time Frame. Baseline and 16 weeks.

Brief Description. Using published methods, IFN scores will be calculated using RNA-seq from whole blood RNA. A two-sided, paired Student's t-test will be used to determine the significance of any changes observed.

Name. Change in IGA.

Type. Secondary Endpoint.

Time Frame. Baseline and 16 weeks.

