As described above, our study doctors will monitor AEs and assign a likelihood that they are attributable to Tofacitinib treatment. Published safety data for Tofacitinib for treatment of RA in typical people indicates 9.4 serious adverse event (SAEs)/100 patient years (all SAEs, treatment-related or not) (109). Given that our trial aims to enroll 47 participants for 16 weeks of treatment (though we anticipate up to seven participants would be lost to attrition at various times during the treatment course) for a maximum total of 14.5 patient years of treatment, a comparable number of SAEs is 1.36. Accordingly, and with the knowledge that our population may be more prone to AEs in general without any treatment due to other health conditions, we define the success of our primary endpoint associated with this aim as no more than two SAEs *definitely related* to treatment during the 16-week trial.

For the purposes of ongoing safety monitoring during the optional Extension Arm and after the initially planned 14.5 patient years of treatment time, we will transform this endpoint of "no more than two SAEs definitely related to treatment during the 16-week trial" to an allowable *rate* and apply the same criteria for overall stopping rules. Accordingly, 2 allowable SAEs definitely related to Tofacitinib over the course of 14.5 patient years translates to a rate of 13.83 SAEs/100 patient years (see stopping rules #5 and #6).

Research Methods for Specific Aim 2. To determine the impact of JAK inhibition on the immune dysregulation caused by trisomy 21.

Our results demonstrate that individuals with T21 show obvious signs of immune dysregulation and hyperactivation of IFN signaling at the levels of mRNA signatures, cytokine profiles, and plasma metabolites. In this Specific Aim, we will define whether these inflammatory markers can be driven by Tofacitinib toward values observed in typical people. Importantly, we have already defined the directionality and average

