The bulk of all clinical activities and study visits will take place at the CU Medicine Colorado Translational Research Center (CTRC). The CTRC provides private, quiet exam rooms to CU-Anschutz researchers for free. Audiograms and chest x-rays will be performed at the UCH Hospital on the CU-Anschutz campus. Cognitive assessments will be performed in a private room at the Linda Crnic Institute. Clinical labs and autoantibody assessments will be performed at the UCH Clinical Laboratory. All researcher labs, offices, and facilities involved in the clinical trial are located at CU-Anschutz and are within a five-minute walk of each other. Blood draws will be performed by qualified phlebotomists who have extensive experience with participants with DS. Participants and their representatives are accompanied to the CTRC by a clinical coordinator, who will then communicate with a member of the laboratory team for the timely transfer of the tubes containing the blood.

In addition to the study visits and activities and AE monitoring described in detail above, existing medical records will also be accessed during the trial. All data will be given an alphanumeric, randomly generated Study IDs and will be stored in HIPAA-compliant password and access restricted programs, such as REDCap. The linker key for identification of participant names corresponding to Study IDs will be access restricted to select members of the clinical team who need this information for job related duties. As such, the resulting coded information available to investigators is considered de-identified in accordance with HS.gov guidance (<https://www.hhs.gov/hipaa/for-professionals/privacy/special-topics/de-identification/index.html#specificstudies>). This study will use University mandated web-based study scheduling module called Oncore, that uses participant level identifiable information to integrate scheduling, financial, and study visit tracking information.

From coded blood samples, our laboratory team will separate plasma, white blood cells (WBCs), and red blood cells (RBCs), and will generate various molecular and cellular datasets, including transcriptome data from WBCs (RNA-seq), cytokine data (MSD assays), metabolomics data, and autoantibody data. All coded clinical and molecular data will be stored in HIPAA-compliant a central data repository hosted by the CU-Anschutz School of Medicine Information Technology Office.

Risks, Protections from Risk, and Justifications.

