Specific Aim 3. It is possible that some skin conditions will be more sensitive to JAK inhibition than others. For example, in our experience, AD, the most common of the evaluated conditions among those with T21, is more likely to respond rapidly to JAK inhibition than vitiligo. If this proves to be the case during the initial 10-participant phase, we may revise our inclusion criteria for the remainder of the trial to maximize recruitment of individuals that will experience a clinical benefit within 16 weeks of treatment. It is also possible that we will have responders and non-responders even within the same immune skin condition. Although this would dilute our chances of reaching our endpoints, it could be nonetheless very informative to identify differences in IFN scores, cytokines, metabolites or other clinical variables among the two groups, which would inform the design of follow up trials.

Specific Aim 4. It is possible that changes in cognition may not be discerned during the relatively short time course of treatment. Also, it is possible that not all participants will be able to complete all tasks. However, we have taken steps to minimize these risks associated with a short treatment window by selecting measures that are scalable and highly sensitive to change. We have addressed the attrition concern by selecting measures that are developmentally engaging, brief, and easy to administer, thus reducing threats to validity based on participant motivation issues. Furthermore, to address confounding issues observed in previous DS assessment work, each task specifically minimizes motor, expressive language, and receptive language demands, all areas of pronounced challenge in DS. The proposed assessments, therefore, strike a balance between the most advanced approaches to characterizing cognition while maintaining a high degree of feasibility of administration and minimizing phenotype specific threats to validity and reliability. Nevertheless, during the initial 10-participant phase we will explore other instruments driven by new findings related to DS outcome measure validation.

VII. Data Analysis Plan:

Specific Aim 1. To define the safety profile of JAK inhibition in people with Down syndrome.

Primary Endpoint: Evaluate the safety of Tofacitinib in people with Down syndrome.

Endpoint Definition: no more than two serious adverse events (SAE) *definitely* related to treatment during the 16-week study period (see *Data and Safety Monitoring Plan*).

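### Participants who fall silent are closed as lost without a required check for serious events, so time not observed in effect counts as event-free in the primary safety count

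*Combined protocol and SAP*

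**What the plan says.** **Closure.** Under Participant Discontinuation and Trial Stopping (section IV.C), individual rule 8 ends with: "After a total of five unreturned communications, the participant will be considered lost to follow-up and no further contact attempts will be made". The rule asks for no SAE query, vital-status check or record review.

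**Endpoint.** Outcome Measures sets the primary safety criterion: "we calculate that we should have no more than two serious adverse events (SAE) definitely related to treatment over the course of 16-weeks". Research Methods for Specific Aim 1 and the Data Analysis Plan repeat it as a count. Trial stopping rule 5 is triggered when more than two such events are reported within 14.5 patient-years. Rule 6 applies after that, as a rate above 13.83 per 100 patient-years.

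**Derivation of the limit.** The reference source "indicates 9.4 serious adverse event (SAEs)/100 patient years (all SAEs, treatment-related or not"). The exposure is stated as a "maximum total of 14.5 patient years of treatment, a comparable number of SAEs is 1.36". The same sentence allows for losses: "though we anticipate up to seven participants would be lost to attrition at various times during the treatment course".

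**Event capture.** Safety and Adverse Event Monitoring runs the recording window to the visit two weeks after the last dose, or to the final Extension Arm visit. It describes events reaching staff through participant report, visits and laboratory review. Section V, Description of Procedures, adds to this that "existing medical records will also be accessed during the trial", without giving a purpose or timing. The COVID-19 section allows extra record requests about an illness, but these are optional and only for participants still enrolled.

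**The concern.** The ordinary routes by which an SAE reaches the study stop when contact stops, and rule 8 puts nothing in their place. The recording window stays open on paper for a lost participant, but nobody is told to fill it. Only a study doctor can classify an event as definitely related, and an event never seen cannot be classified.

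The limit is a fixed count. Losses shorten the observed time and lower the expected count, but the limit of two stays where it was. The error has one direction: missed events can make the drug look safer, never less safe.

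Death, life-threatening events and hospitalization are SAE criteria and also possible reasons for silence, so loss may be related to the outcome. The primary safety conclusion turns on a single event, since two meet the criterion and three do not.

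**Working it through.** **Inputs.** 47 participants, 16 weeks, 9.4 SAEs per 100 patient-years, a limit of two, and up to seven losses (Research Methods for Specific Aim 1). The week of loss, the share of losses closed under rule 8 and the true event rate are not given, so they are assumptions shown over a range.

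**1. The plan's own figures.**
- Exposure: 47 × 16/52 = 14.46 patient-years (stated 14.5).
- Expected SAEs: 14.46 × 9.4/100 = 1.36 (as stated).
- Limit as a rate: 2/14.46 × 100 = 13.83 per 100 patient-years (as stated).
- Attrition: 7/47 = 14.9%.

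All reproduce. The 14.46 gives every participant the full 16 weeks.

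**2. Observed time if all seven are lost and nothing is learned afterwards.** Observed patient-years = 40 × 16/52 + 7 × t/52, where t is the week of loss.

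| Week of loss | Observed patient-years | Share unobserved | Two events, per 100 patient-years |
|---|---|---|---|
| 12 | 13.92 | 3.7% | 14.4 |
| 8 | 13.38 | 7.4% | 14.9 |
| 0 | 12.31 | 14.9% | 16.25 |

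In each row two observed events satisfy the count, although the rate over observed time exceeds 13.83.

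**3. Chance of meeting the limit when loss is unrelated to events.** Poisson probability of two or fewer, with mean = rate × observed patient-years/100.

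| True rate per 100 patient-years | Full follow-up | Seven lost at week 12 | at week 8 | at week 0 |
|---|---|---|---|---|
| 9.4 | 0.843 | 0.855 | 0.867 | 0.889 |
| 20 | 0.448 | 0.473 | 0.499 | 0.554 |

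At week 8 the gain is 0.867 − 0.843 = 2.4 points at a rate of 9.4, and 0.499 − 0.448 = 5.1 points at 20. With only one loss, at week 8, the gains are 0.4 points (0.847 − 0.843) and 0.7 points (0.455 − 0.448).

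**4. If loss is related to events.** Seven losses at week 8 leave 7 × 8/52 = 1.08 patient-years unobserved. The chance of at least one unseen SAE is 1 − exp(−0.094 × 1.08) = 0.10 at the reference rate. It is 0.26 if lost participants have three times that rate. The multiple of three is an assumption.

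**5. Conditional view.** Suppose exactly three definitely related SAEs truly occur and each is missed with probability m. The count then reads two or fewer with probability 1 − (1 − m)³. Taking m as the share of exposure unobserved, seven losses at week 8 (m = 7.4%) give about 21%, and one such loss (m = 1.1%) gives about 3%.

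**The case against.** The strongest reply is that the plan leaves room for the check. Rule 8 ends contact attempts; it does not bar a chart review. Section V provides for record access, and the reporting rules apply to any SAE that a coordinator or doctor discovers, by whatever route. Every participant must have a study partner or guardian at every visit, and rule 8 uses contact details from either of them. A hospital admission or death therefore need not silence both, which makes event-caused loss less likely. Monthly reports cover retention and deaths, Annual Reports give reasons for dropout, and the interim review considers data loss. The endpoint definition also points to a Data and Safety Monitoring Plan that was not among the documents, and it may hold an ascertainment rule.

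Much of this stands, and it rules out several stronger readings that a reader might infer:
- *That records are never searched.* Section V allows access. What is missing is a requirement that links it to lost participants and the recording window.
- *That the plan declares lost participants event-free.* It is silent; that is the practical effect of a raw count.
- *That one missed event defeats both numerical stopping rules.* Rule 6 is a rate: three events in 22 patient-years give 13.6, below 13.83. Other stopping grounds need no count at all.
- *That the chance of a false pass is 38% or more.* In the conditional formula, 38% needs m = 14.9%, which treats all seven losses as rule 8 closures at week 0. The plan expects losses at various times, and attrition also includes exits for adverse events that the study already knows about. A figure of 66% needs m = 30%, which has no basis in the documents.

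The reply does not supply a required step. Access described as additional to adverse event monitoring, with no stated purpose, does not oblige anyone to look.

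**Conclusion.** The gap is real and the likely effect modest. Following the plan as written, the primary safety count and stopping rule 5 can only under-count SAEs among participants closed under rule 8. With seven losses unrelated to events, the chance of meeting the limit rises by about 1 to 5 points at a true rate of 9.4 and about 2 to 11 points at 20, depending on when loss occurs.

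These figures rest on a Poisson count, on every anticipated loss being unascertained, and on counting the whole remainder of the 16 weeks. The last two make them upper-end values for losses unrelated to events: fewer participants may be closed under rule 8, and drug exposure after loss is limited to supply already dispensed. The 9.4 is an all-cause rate, and the documents give none for definitely related SAEs, so the probabilities are illustrative. Event-related loss would raise them. One conclusion needs no rate: when two events have been observed, a single unseen definitely related event reverses the primary safety result.

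The absence of a rule is judged on the supplied text only. The change is worth making because it is cheap and protects a primary endpoint.

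**What to change.** **Rule 8.** Before closure, and within the consent authorization, require a query to the study partner or guardian, an Epic search and a records request to the treating provider. The provider request matters because out-of-state participants may have no local record of an admission. The check covers death, hospitalization and other SAEs through two weeks after the last dose that the dispensed supply would allow. A study doctor classifies any SAE found, and those judged definitely related count in the primary endpoint and in trial stopping rules 5 and 6. If the Data and Safety Monitoring Plan already contains such a rule, cite it here instead.

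**Data Analysis Plan, Specific Aim 1.** Report observed patient-years beside the count, and the number of participants whose SAE status is unknown. State how many unseen definitely related SAEs would reverse the result. This tipping-point statement is preferable to assigning one event to each participant of unknown status, which would fail the endpoint automatically at three such participants whatever the data showed.

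**Cost.** A chart and provider check for at most about seven participants in the planned 16-week cohort, a few sentences of text, and a safety count that may turn out less favourable. Provider requests outside the local system will take some effort, and an event known only from a chart may often be rated possibly related and leave the count unchanged.
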